## 2.9 Statistical analysis

All data will be analyzed according to intent-to-treat principles. Continuous data were reported as means  $\pm$  standard deviation and were analyzed using one-way ANOVA or Kruskal-Wallis tests as appropriate. Categorical data were presented as frequency and percentages and were analyzed using the chi-squared test. A repeated-measures ANOVA was performed for 3-time points to evaluate the effect of group factors, time factors, and the interaction between time  $\times$  group on the outcomes variables. A simple effect test was used to examine the difference among groups within each time point and between the 3-time points within each group when the interactions of time  $\times$  group were significant. All statistical tests were two-sided, and statistical significance was considered at  $p < 0.05$ .

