## 2 Methods

### 2.1 Study design

This single-center, single-blind trial. All participants will be recruited from Xuanwu Hospital, Capital Medical University, Beijing. This study will be reported in accordance with both the CONSolidated Standards of Reporting Trials (CONSORT) statement and the CONSORT statement for nonpharmacological interventions.

The participants will be randomized into either a NLCs training group or a home-based training group. Both groups will undergo 72, 1-hour sessions of NLCs training or 144, 30-minute sessions of home-based training across 12 months. The outcomes will be assessed at baseline, at 6-month and 12-month follow-up. The outcomes will include multiple neuropsychological assessments to examine the effect of NLCs training on cognitive functions, resting-state EEG to measure brain connectivity and neural activity.

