### **Randomization**

Participants will be randomly allocated to either the intervention group or the control group in a ratio of 1:1. After participants have given their informed consent, randomization will be performed by an independent statistician who is blinded to the patient interventions using IBM SPSS Statistics Software following the sequence: Data/select cases/random sample of cases/exact 1 case of the 2 total cases. Afterwards, the sealed randomization codes and intervention number are sent out to each center.

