### **Blinding**

Radiologists, statisticians, and neuropsychologists who measure the outcomes will be blinded to the randomization status. Blinding will also be maintained for data management, outcome assessment, and data analysis. Participants and therapists cannot be blinded to the intervention they receive or provide.

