### 2.5.3 Primary outcome

The primary outcome measure is the score change in MMSE from baseline to the end of the intervention.

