## 2.8 Sample size

There are no published randomized controlled trials on NLCs cognitive training or home-based cognitive training in MCI patients. In our preliminary experiments, the intervention resulted in improvement in MMSE scores (mean: 0.5 vs 0.04). According to these data, to obtain a statistical power of 90% with a significance level of 5%, the sample size needs to be 26 for each group. To allow for a maximum dropout rate of 20%, the sample size is set to 32 participants in each group.

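### Intent-to-treat is promised but not made operational: no analysis set or missing-data method is given, so the primary 12-month MMSE comparison, run as written, is a complete-case analysis

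*Combined protocol and SAP*

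**What the plan says.** Section 2.9 (Statistical analysis) states the principle once: "All data will be analyzed according to intent-to-treat principles". It then names the tests. Continuous data "were analyzed using one-way ANOVA or Kruskal-Wallis tests as appropriate". For the longitudinal data, "A repeated-measures ANOVA was performed for 3-time points to evaluate the effect of group factors", time and their interaction, with simple-effect tests if the interaction is significant.

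Section 2.5.3 sets the endpoint: "The primary outcome measure is the score change in MMSE from baseline to the end of the intervention". Section 2.1 sets the visits: "The outcomes will be assessed at baseline, at 6-month and 12-month follow-up", and Table 1 in section 2.6 schedules MMSE at each of them.

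Loss to follow-up appears only in section 2.8: "To allow for a maximum dropout rate of 20%, the sample size is set to 32 participants in each group". Nowhere does the protocol define an analysis set or mention missing data, imputation, a mixed model, a sensitivity analysis, or assessment of people who stop training.

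**The concern.** The named tests do not deliver the stated principle by themselves. A 12-month change score cannot be computed without a 12-month score, so a one-way ANOVA or Kruskal-Wallis test on it omits that person. Repeated-measures ANOVA over three time points, in its standard form, omits anyone who lacks any one of the three. A separate test at month 6 would use the 6-month scores of people lost later, but those scores would not inform the 12-month contrast.

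A completers-only comparison no longer compares the groups that were randomised. It is biased if outcome-related dropout differs between the arms. Such a difference is plausible here: training lasts 12 months, one arm attends a clinic while the other trains at home, and "Participants and therapists cannot be blinded to the intervention they receive or provide". With no rule set in advance, the choice between complete cases, carrying values forward and imputation could also be made after the data are seen.

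**Working it through.** **1. The plan's dropout figure.** Section 2.8 starts from 26 per group and allows for 20% dropout.
- 26 × 1.20 = 31.2, rounded up to 32, which is the stated figure. (26 / 0.80 = 32.5 would give 33.)
- 32 × 0.80 = 25.6, so the planned 26 is in effect a completer count. The allowance protects that count but does not say how dropouts enter the analysis.

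**2. How many are left out.** The Abstract, section 2.1 and Randomization ("Participants will be randomly allocated to either the intervention group or the control group in a ratio of 1:1") describe two arms, so 64 are randomised.
- 64 × 0.20 = 12.8, about 13. This is a ceiling: it takes every dropout to lack a 12-month MMSE.
- If the traditional programme described under Intervention were a third arm, the count would be 96 × 0.20 = 19.2, about 19.

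**3. SD of change.** Section 2.8 gives no SD. Its means (0.5 and 0.04) differ by 0.46. With 26 per group, 90% power and two-sided 5%, SD = 0.46 × √(26/2) / (1.960 + 1.282) = 0.512, or 0.502 by the t distribution. I use 0.502.

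**4. Illustration of possible bias.** Assumed inputs, none from the documents except the difference and the dropout rate:
- true 12-month difference 0.46, and SD of change 0.502 at both visits;
- 20% dropout per arm, all after month 6;
- in one arm only, dropout odds multiplied by e for each SD of worse 6-month change; in the other arm dropout is random.

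Under normality, completers in the selective arm then have a mean 6-month change about 0.173 SD above their arm's true mean. The shift carried to 12 months is r × 0.173 × 0.502, where r is the correlation between the 6- and 12-month changes.

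| r | Shift | Estimate, home arm selective | Estimate, NLC arm selective |
|---|---|---|---|
| 0.2 | 0.017 | 0.443 | 0.477 |
| 0.5 | 0.043 | 0.417 | 0.503 |
| 0.8 | 0.070 | 0.390 | 0.530 |

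If both arms select alike, the shifts cancel and the estimate stays at 0.46. The shift in points is proportional to the SD, so it inherits the uncertainty in step 3.

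**5. When the 6-month scores help.** The scenario in step 4 lets dropout depend on an observed 6-month score. A likelihood-based model that uses those scores is then valid and recovers 0.46. If the same people leave before month 6, that score is never seen. In a simulation of that case (home arm selective, within-person correlation 0.97), the complete-case estimate was 0.421 and the modelled one 0.422, so the model removed almost none of the bias. With half leaving early, the modelled estimate was 0.442.

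**6. How robust a positive result would be.** The critical difference at 26 per group is 2.009 × 0.502 × √(2/26) = 0.280. Suppose only the missing 20% of the NLC arm did worse than its completers, using the completer standard error:
- an observed 0.46 loses significance at (0.46 − 0.280) / 0.20 = 0.90 points worse, or 1.8 SD;
- an observed 0.35 loses it at (0.35 − 0.280) / 0.20 = 0.35 points worse, or 0.7 SD.

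**The case against.** The strongest reply accepts the omission and disputes its weight.

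- **Dropout is undefined.** Section 2.8 does not equate it with a missing 12-month MMSE, and section 2.7 speaks of evaluating all participants without requiring adherence. This stands, and is why 13 of 64 is given as a ceiling.
- **The bias is hypothetical.** It needs fairly strong selection in one arm and none in the other, and the SD is back-solved. This stands. A reader might infer that the primary result will be biased, or biased in favour of the clinic. The documents give no dropout pattern by arm, and the illustration moves the estimate either way.
- **A result of the planned size is fairly robust.** This stands for 0.46, but much less for 0.35.
- **The mixed model is no complete remedy.** This stands: it gains little for people lost before month 6, and the documents do not say when dropout will occur.
- **Power.** A reader might infer that the change would raise power noticeably. The documents do not support that. The gain comes mostly from baseline adjustment, with a standard-error ratio of √((1 + ρ)/2), where ρ is the within-person correlation. At ρ = 0.6 the ratio is 0.894, but with an SD of change of 0.502 this implies a cross-sectional MMSE SD of only 0.502 / √(2 × 0.4) = 0.56. If that SD were 2 (an assumption), ρ would be 1 − 0.502² / (2 × 2²) = 0.97 and the ratio 0.99, almost no gain. The documents give neither quantity.

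The larger sample size does not answer the point, because recruiting more people is not a rule for analysing those who are lost.

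**Conclusion.** The point holds. Section 2.9 promises intent-to-treat, the protocol gives no analysis set or missing-data method, and the named tests are complete-case unless values are imputed. Up to about 13 of 64 randomised participants would be missing from the primary comparison, and the 6-month scores of those lost later would not contribute to it.

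Confidence is high for the omission, which rests on the text and on how the tests work. It is lower for the size of any bias: the range of about 0.39 to 0.53 around a true 0.46 rests on the assumed one-arm dropout pattern and the SD inferred from 2.8, and the bias is about zero if the arms lose people in the same way. No gain in power is claimed. This is a cheap improvement that should be made, not a defect shown to distort the trial.

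**What to change.** In section 2.9:

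1. Define the analysis set as all randomised participants, analysed as allocated.
2. Replace the complete-case ANOVA as the primary analysis with a likelihood-based mixed model for repeated measures on all available MMSE values, with the 12-month arm difference in change from baseline as the primary contrast. Multiple imputation using baseline and 6-month MMSE, followed by ANCOVA, is an acceptable alternative. Constraining the arms to a common baseline mean is optional.
3. Keep the complete-case ANOVA and add one delta-adjusted (tipping-point) analysis, both as sensitivity analyses.
4. State that the model corrects only for dropout that depends on observed scores. That limit is the reason for the delta-adjusted analysis.

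The cost is one paragraph and a little more analysis work, with no new visits or measures. Because the Abstract describes the trial as ongoing, the change should be a dated amendment made before outcomes are compared by arm.

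### Section 2.9 names no primary test for the MMSE change to month 12 and gives no missing-data method to support its intent-to-treat statement

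*Combined protocol and SAP*

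**What the plan says.** Section 2.5.3: "The primary outcome measure is the score change in MMSE from baseline to the end of the intervention". Section 2.1 sets the intervention at 12 months and the visits: "The outcomes will be assessed at baseline, at 6-month and 12-month follow-up". It also sets the comparison: "The participants will be randomized into either a NLCs training group or a home-based training group".

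Section 2.9 is the only analysis text. It mentions neither MMSE nor a primary test. It contains:

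- a general sentence for continuous data, which "were analyzed using one-way ANOVA or Kruskal-Wallis tests as appropriate", with no outcome, visit or rule for choosing between the two tests;
- a longitudinal model: "A repeated-measures ANOVA was performed for 3-time points to evaluate the effect of group factors, time factors, and the interaction between time" and group, applied to the outcomes in general;
- a follow-up step: "A simple effect test was used to examine the difference among groups within each time point". This step, and the comparison of visits "within each group when the interactions of time" and group, are made only if that interaction is significant;
- an analysis principle: "All data will be analyzed according to intent-to-treat principles". No imputation, likelihood-based model or rule for a missed visit follows it.

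All tests are two-sided at 5%. No baseline covariate is named. Section 2.8 plans for mean MMSE improvements of 0.5 and 0.04, 90% power, 26 per group, and 32 per group after allowing for 20% dropout. It gives no SD.

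**The concern.** The primary outcome is one contrast: the group difference in MMSE change at month 12. Section 2.9 offers two routes towards it and labels neither as primary.

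- The general ANOVA or Kruskal-Wallis sentence could be applied to change scores, with no preceding test.
- The repeated-measures ANOVA yields a group main effect that averages in the baseline visit, a 2-df interaction that mixes months 6 and 12, and a by-visit comparison that is unadjusted and conditional on the interaction.

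Two things are at stake. The first is power: if the conditional route is followed, the 90% planned in section 2.8 may not be delivered. The second is that the test on which the trial is judged remains open until the data are seen. Separately, classical repeated-measures ANOVA, as usually fitted, drops anyone who misses a visit. Nothing in section 2.9 says how such participants stay in an intent-to-treat analysis.

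**Working it through.** **Inputs.** From section 2.8: difference 0.5 − 0.04 = 0.46 points, 26 per arm before dropout, 32 after, 90% power, 5%. From section 2.9: two-sided tests, three visits. Assumed, because the documents do not give them: compound symmetry, correlation ρ between visits of 0.3 to 0.8, and a difference building linearly (0, 0.23, 0.46).

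**The plan's own figure.** The 26 per group cannot be reproduced without an SD. Solving backwards (two-sample t, 26 per arm, two-sided 5%, 90% power) gives a standardised effect of 0.917, so change SD = 0.46/0.917 = 0.502. The raw SD is then 0.502/√(2(1−ρ)), that is 0.42 at ρ = 0.3 and 0.79 at ρ = 0.8. Both are below one point on a 0–30 scale, so larger SDs are shown as well.

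**Formulas.**

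- Change contrast: t on 50 df with the change SD.
- Baseline-adjusted contrast: residual SD = change SD × √((1+ρ)/2). At SD 0.502 this is 0.405 (ρ = 0.3) or 0.476 (ρ = 0.8). Closed-form power is 98.0% and 92.7%; simulation gives 97.9% and 92.4%.
- Interaction: F on 2 and 100 df with noncentrality 26 × Σ(dᵢ − d̄)²/(change SD)². For (0, 0.23, 0.46) the sum is 0.1058, so 26 × 0.1058/0.2517 = 10.93 and power is 84%.
- Conditional month-12 test: both the interaction and the unadjusted month-12 comparison must be significant. The latter alone has 97% (ρ = 0.3) or 54% (ρ = 0.8), so joint power cannot exceed 84% or 54%. Simulation gives 83% and 48%.

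**Power for 0.46 points at month 12, linear build-up** (ranges run from ρ = 0.3 to 0.8)

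| Change SD | Conditional month-12 test | Interaction | Change contrast | Baseline-adjusted |
|---|---|---|---|---|
| 0.50 | 83% to 48% | 84% | 90% | 98% to 92% |
| 1.0 | 22% to 8% | 29% | 37% | 52% to 40% |
| 2.0 | 5% to 2% | 10% | 13% | 17% to 14% |

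**Other trajectories, SD 0.50.**

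- Full 0.46 at both months: the sum is 0.46² × 2/3 = 0.1411, noncentrality 26 × 0.1411/0.2517 = 14.57, interaction power 93%. That equals the adjusted contrast at ρ = 0.8. The conditional test is still weak at that correlation, about 51%.
- Effect at month 6 only (0, 0.46, 0): the sum and noncentrality are the same, so the interaction rejects in about 93% of trials although the month-12 difference is zero.

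**False positives (simulated).**

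- Conditional month-12 claim: 0.5% to 1.1% with no effect at any visit; 4.4% to 4.7% with an effect at month 6 only (SD 0.50).
- If the main effect or the interaction could each count as success: about 10%. If a change-score test could count too: about 12%. Neither figure depends on the SD.

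**Dropout.** 20% of 64 = 12.8, about 13 participants. Suppose there is no true effect, one arm's dropouts come from below the median month-6 change (mean −0.798 SD), and the other arm's are random. Month-6 and month-12 changes correlate 0.5 under compound symmetry. Completer bias is then 0.2 × 0.798/0.8 × 0.5 = 0.0997 change SD, and simulated two-sided false positives are 6% to 7%. With the same pattern in both arms, bias is about zero and the rate about 5%. A model valid under missing-at-random removes the one-arm bias. If one arm's dropout depends instead on the unseen month-12 change, completer bias is about 0.20 SD and such a model still leaves 0.13 to 0.15 SD.

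**The case against.** The strongest reply is that the plan already contains an adequate test. Section 2.5.3 defines a change score, and the general sentence in section 2.9 gives continuous data a one-way ANOVA with no condition attached. For two groups that is the two-sample t-test on change, with 90% power at the back-solved SD, and the loss on the conditional route never arises. This stands as a possible reading. Section 2.9 does not say that the sentence covers the primary outcome, so the choice stays open.

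A reader might infer more than the documents support:

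- *That the trial runs at a 10% to 12% error rate.* This needs a rule under which any of several tests counts as success. Section 2.9 states no such rule, and the one sequence it describes is conservative.
- *That the by-visit comparison targets the wrong quantity.* Under 1:1 randomisation the month-12 difference in levels estimates the same effect as the difference in change. Baseline adjustment gains efficiency; it does not correct a bias.
- *That the adjusted contrast is always the most powerful.* If the effect is complete by month 6, the interaction can match it, though without isolating month 12.
- *That section 2.9 contradicts intent-to-treat.* It nowhere excludes incomplete participants. Exclusion would come from the usual way of fitting the method, so what is shown is an omission.

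**Conclusion.** The point holds as a gap in specification, and a cheap one to close. Section 2.9 designates no primary test for the month-12 MMSE change. Its only explicit by-visit comparison is unadjusted and conditional on a 2-df interaction, and it has no missing-data method.

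If the conditional route is used, the cost under linear build-up at change SD 0.50 is 7 to 42 percentage points of power against a change contrast (90 − 83 and 90 − 48). Against a baseline-adjusted contrast it is 15 to 44 (98 − 83 and 92 − 48). These sizes rest on the back-solved SD, compound symmetry and the assumed trajectory. At SD 1.0 or more every option is underpowered, so the choice of test is no remedy for a larger SD. Bias from dropping incomplete participants is modest in the cases examined, takes its direction from the arm with selective dropout, and is about zero if dropout is alike in both arms. That the primary test is unnamed depends on none of these assumptions.

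**What to change.** Rewrite the paragraph in section 2.9:

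1. Name one primary analysis: the two-sided 5% between-group difference in MMSE at month 12, adjusted for baseline MMSE and not conditional on the interaction, from a mixed model using all available visits of all randomised participants. A baseline-adjusted ANCOVA with a stated missing-data method would also serve.
2. State the missing-at-random assumption and add one sensitivity analysis that departs from it.
3. Make the repeated-measures ANOVA supportive, and do not use its group main effect as evidence of efficacy.
4. Date the change before any unblinded analysis.

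The cost is a new paragraph and a little more analysis work, with no new data or participants. The drawback is reliance on missing-at-random, which the sensitivity analysis has to probe. The number of groups also needs reconciling, since section 2.1 and the Randomization section name two while the Intervention section describes a further, traditional condition. That is a separate point and is not counted here.

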### **2.2.1 Inclusion criteria**

1. Subjects with informed consent;
2. Literate Han Chinese, above the age of 18;
3. At least 6 years of education;
4. Neither normal nor demented according to the criteria of the Diagnostic and Statistical Manual of Mental Disorders, Fourth Edition, with a Clinical Dementia Rating(CDR)  $\geq 0.5$  on at least one domain and a global score  $\leq 0.5$ ; a Mini-Mental State Examination score  $\geq 20$  (primary school), or  $\geq 24$  (junior school or above).
5. having normal vision and hearing with/without corrective devices.

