## 2.6 Data collection

Inclusion and exclusion criteria will be assessed at screening. After written informed consent is acquired, the following data will be collected: demographic data (gender, age, education, and occupation); medical history; concomitant medications; and findings from a complete physical examination and neurological examination. Then, neuropsychological assessments, and EEG will be carried out. The follow-up assessments will be scheduled at 6-month and 12-month after intervention. The study schedule of the trial is shown in Table 1. The study flowchart is presented in Figure 1.

Table 1 Schedule of the trial

Time point	Study period			
	screening	baseline	6-month intervention	12-month intervention
Eligibility screen	×			
Informed consent	×			
Randomization		×		
Demographic data		×		
CDR	×			
Assessments				
MMSE	×	×	×	×
MoCA		×	×	×
WHO-UCLA AVLT		×	×	×
BNT		×	×	×
IADL		×	×	×
BI		×	×	×
HARS		×	×	×
GDS		×	×	×
CMAI		×	×	×
NPI		×	×	×
ZBI		×	×	×
EEG		×	×	×

[figure not shown]

FIGURE 1 The flowchart of this trial

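### Age and education are recorded, and schooling sets the MMSE entry floor, but neither allocation nor analysis uses them: a modest, avoidable loss of precision

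*Combined protocol and SAP*

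**What the plan says.** Eligibility (2.2.1) covers "Literate Han Chinese, above the age of 18", with at least 6 years of education. The MMSE floor depends on schooling: 20 for primary school, 24 for junior school or above. No upper age limit is given.

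Allocation (Randomization) is simple: "Participants will be randomly allocated to either the intervention group or the control group in a ratio of 1:1". No stratification or minimisation factor is named.

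Baseline data (2.6) include "demographic data (gender, age, education, and occupation".

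The analysis (2.9) uses one-way ANOVA or Kruskal-Wallis tests for continuous data, plus a model described as follows: "A repeated-measures ANOVA was performed for 3-time points to evaluate the effect of group factors, time factors, and the interaction between time" and group. If the interaction is significant, simple-effect tests compare the groups at each visit. No covariate is named anywhere in 2.9.

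The primary outcome (2.5.3) is the change in MMSE from baseline to the end of the intervention. The target comes from pilot data (2.8): "the intervention resulted in improvement in MMSE scores (mean: 0.5 vs 0.04", a difference of 0.46 point in mean improvement.

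**The concern.** The protocol treats MMSE as dependent on schooling when it decides who may enter, then ignores schooling when it compares the arms. There is also some reason to think schooling could be related to change. MMSE stops at 30 (2.5.1), so a primary-school entrant at the floor has 10 points of room, and an entrant with more schooling at the floor has 6. Only primary-school participants can enter with scores of 20 to 23.

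With 26 to 32 per arm and no strata, the arms can differ noticeably in schooling or age by chance. Whatever outcome variance these two factors explain stays in the error term. Without a prespecified adjustment, an imbalance seen in the baseline table also invites one chosen after the fact.

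**Working it through.** **The plan's own figure.** Section 2.8 states that "the sample size needs to be 26 for each group" for 90% power at 5%; in 2.9, "All statistical tests were two-sided". No SD is given, so 26 cannot be reproduced forwards. Solving backwards with the normal approximation:

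SD = 0.46 / [(1.960 + 1.282) × √(2/26)] ≈ 0.51 point of change.

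This is used below only as the plan's implied value.

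**How often schooling is imbalanced.** The primary-school share is not in the documents; 20 to 50% is assumed. Allocating 64 participants at random, 32 per arm (hypergeometric):

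| Assumed share | Gap of 15 or more percentage points | Gap of 20 or more |
|---|---|---|
| 20% (13 of 64) | 21% | 6% |
| 30% (19) | 27% | 10% |
| 40% (26) | 20% | 7% |
| 50% (32) | 21% | 8% |

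These count gaps in either direction.

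**Effect on MMSE level.** Shift = (difference between stratum means) × (gap in share). If the stratum means differ by 3 points (assumed), a 15-point gap gives 3 × 0.15 = 0.45 point. This applies to the group main effect and the per-visit simple effects, which use levels.

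**Effect on MMSE change, the primary outcome.** A constant level difference cancels, both in the change score and in the time × group term. Only a difference between strata in mean change carries over:

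- 0.5 point (assumed) × 0.15 = 0.075, or 16% of 0.46.
- 1 point (assumed) × 0.15 = 0.15, or 33% of 0.46.

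The implied SD sets a ceiling. The between-strata variance p(1−p)g² cannot exceed 0.51², so the difference g in mean change is at most 0.51/√(0.2 × 0.8) ≈ 1.28 at a 20% share and 0.51/0.5 ≈ 1.02 at 50%. A one-SD imbalance, √(2p(1−p)/32), then shifts the result by at most 0.51 × √(2/32) ≈ 0.13 point, which equals the whole standard error at 32 per arm. The 1-point case is therefore near the limit. If the true SD of change is larger, the possible shift is larger.

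**Precision.** With 26 per arm analysed there are 52 − 2 = 50 residual degrees of freedom, and 48 after adding age and education. The SE ratio is √[(1 − R²) × 50/48], where R² is the share of residual variance explained:

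- R² = 0.10: √0.9375 = 0.968; equivalent n = 26/0.9375 = 27.7 per arm.
- R² = 0.20: √0.8333 = 0.913; equivalent n = 26/0.8333 = 31.2 per arm.
- Break-even: 1 − R² = 48/50, so R² = 0.04.

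Counting baseline MMSE as already in the model (49 and 47 degrees of freedom) gives 0.969 and 0.913, essentially the same. No R² is given in the documents, so 10 to 20% is an assumption.

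**The case against.** The strongest objection is that chance imbalance under randomisation is not bias. It is already reflected in the standard error, it does not by itself raise the type I error, and half of the imbalances would work against the intervention arm. This stands, and leaves an efficiency argument only.

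A reader might also infer that an imbalance could rival the 0.46-point target, since 0.45 appears above. The documents do not support that. The 0.45 is a shift in level, while 0.46 is a difference in change, and a constant level difference cancels there. The 4 points in 2.2.1 separate two entry floors, not two stratum means; the 6-year education minimum already cuts off the lowest schooling.

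The efficiency gain is also uncertain. R² may be lower for change than for level, and baseline MMSE may absorb much of what schooling explains. For age the documents give no distribution or slope, so its part cannot be quantified separately.

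What survives is that levels are compared in 2.9, where imbalance enters in full; that the differing floors and common ceiling make a zero relation between schooling and change an unsafe assumption; and that the adjustment is nearly free.

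**Conclusion.** The point holds as one of precision. The plan collects two plausible predictors of its cognitive outcomes, uses one of them to set eligibility, and uses neither in allocation or analysis. On the primary change score, a 15-point schooling imbalance would move the estimate by about 0.08 to 0.15 point under the assumed 0.5 to 1 point difference in change between strata; with no such difference it would not move it at all. Adjustment would cut the standard error by about 3 to 9% if age and education explain 10 to 20% of residual variance, and would gain nothing below about 4%. The documents supply neither the stratum shares nor the variance explained, so these are ranges under stated assumptions. They do not support a claim of bias, of inflated type I error, or of an imbalance in the primary contrast as large as the target effect.

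**What to change.** In 2.9, prespecify the primary comparison as 12-month MMSE (or change to 12 months) by group, adjusted for baseline MMSE, education stratum (primary versus junior school or above, the split in 2.2.1) and age as a continuous variable. State that the baseline-visit MMSE is the covariate, since Table 1 also schedules MMSE at screening. Baseline MMSE must be in the model: a 12-month comparison adjusted for age and education alone could lose the within-person correction that the change score provides. Adding age and education only as main effects to the repeated-measures ANOVA would not help either, because they would not reduce the error term of the time × group test.

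Use the same two covariates, with each scale's own baseline, for MoCA, AVLT and BNT. Report the adjusted between-arm difference with its 95% CI.

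The cost is SAP wording and two further degrees of freedom out of about 50 for age and education. No new data are needed.

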### 2.5.4 Secondary outcome

The secondary outcomes for neuropsychological assessments include the score change from baseline to the 6-month and 12-month after intervention in other scales. The EEG results also dose.

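### Section 2.9: the group main effect of the three-visit ANOVA includes baseline, so it does not estimate the change-from-baseline outcomes and can lose much of the planned power if read as a treatment test

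*Combined protocol and SAP*

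**What the plan says.** Section 2.1 sets the visits: "The outcomes will be assessed at baseline, at 6-month and 12-month follow-up". Table 1 in section 2.6 shows the same three assessments and puts randomization at baseline.

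Section 2.5.3 defines the primary outcome as the change in MMSE from baseline to the end of the intervention. Section 2.5.4 defines the secondary outcomes as "the score change from baseline to the 6-month and 12-month after intervention in other scales".

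For the analysis, section 2.9 states: "A repeated-measures ANOVA was performed for 3-time points to evaluate the effect of group factors, time factors". The same sentence adds the time-by-group interaction. Between-arm comparisons at each visit follow only if that interaction is significant. One-way ANOVA or Kruskal-Wallis is also listed for continuous data, without saying which variable it is applied to. No section says which test or contrast decides the primary outcome, and none says that the group main effect is not an efficacy test.

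**The concern.** In this model the group main effect is the difference between arms averaged over baseline, month 6 and month 12. Baseline carries one third of the weight and no treatment effect, so the average is pulled towards zero. It also carries any chance baseline difference. The outcomes are changes from baseline, so this term answers a different question. The time main effect averages over the arms and says nothing about the difference between them.

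Section 2.9 lists the group effect alongside the interaction without ranking them. When the interaction is not significant, the visit-wise contrasts are not opened, and the group effect is the between-arm result left from this model. A non-significant group effect could then be reported as no benefit, although the term understates the month-12 difference by construction. This applies to MMSE and to every secondary scale analysed this way.

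**Working it through.** **Inputs from the documents.** Section 2.8: "the intervention resulted in improvement in MMSE scores (mean: 0.5 vs 0.04"), a difference of 0.5 − 0.04 = 0.46; "the sample size needs to be 26 for each group"; 90% power at 5%. Section 2.9 makes tests two-sided.

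**Assumed, because the documents are silent.** SD; equal variances and equal between-visit correlation ρ; three effect shapes (only at month 12, linear, full by month 6).

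**1. The plan's own figure.** With no SD stated, 26 cannot be reproduced independently, so I solved for the SD it implies. Normal approximation: 0.46 × √(26 / [2 × (1.960 + 1.282)²]) = 0.46 × √(26/21.0) = 0.512. Noncentral t: 0.502 (standardised difference 0.917). I take 0.502 as the SD of change, so a comparison of month-12 change has 90% power by construction.

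**2. Dilution (needs no SD).** The group main effect estimates the mean of the three visit differences:
- only at month 12: (0 + 0 + 0.46)/3 = 0.15, one third
- linear: (0 + 0.23 + 0.46)/3 = 0.23, one half
- full by month 6: (0 + 0.46 + 0.46)/3 = 0.31, two thirds

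**3. Power of the group main effect.** Visit SD s = 0.502/√(2(1−ρ)). SD of the three-visit mean = s√((1+2ρ)/3). Standard error = that SD × √(2/26), with 50 df. Example at ρ = 0.5: s = 0.502, SD of mean = 0.410, standard error = 0.114. For the late effect the noncentrality is 0.153/0.114 = 1.35, giving 26% power.

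| ρ | Only month 12 | Linear | Full by month 6 |
|---|---|---|---|
| 0.3 | 41.7% | 74.7% | 93.8% |
| 0.5 | 26.3% | 51.0% | 75.4% |
| 0.7 | 15.5% | 28.9% | 46.5% |
| 0.8 | 11.4% | 19.6% | 31.2% |

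**4. Power of the planned interaction.** F test on 2 and 100 df, noncentrality 26 × Σ(δⱼ − δ̄)²/0.502², where δⱼ is the arm difference at visit j; ρ cancels. Late or early effect: Σ = 0.46² × 2/3 = 0.141, noncentrality 14.6, power 93%. Linear: Σ = 2 × 0.23² = 0.106, noncentrality 10.9, power 84%.

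**5. Power with baseline as covariate** (ignoring the one df it uses). Month-12 contrast, residual SD s√(1−ρ²): 98%, 96%, 94% and 93% at ρ = 0.3, 0.5, 0.7 and 0.8. Pooled months 6 and 12, residual SD s√((1+ρ)/2 − ρ²), over the same range of ρ: 52-73% for a late effect, 85-97% linear, 98% or more for an early effect.

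**6. Baseline imbalance.** Each unit of observed baseline difference shifts the expected group estimate by (1+2ρ)/3, which is 0.67 at ρ = 0.5 and 0.87 at ρ = 0.8. Given a chance imbalance of 2 standard errors and no treatment effect, the test statistic has mean 2√((1+2ρ)/3) and SD √(1 − (1+2ρ)/3). It exceeds ±1.96 in about 29% of trials at ρ = 0.5 and 39% at ρ = 0.8. Averaged over all randomizations the rate is still 5%.

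**7. If 0.50 is instead the SD at one visit.** Late, linear and early group-effect power is 26%, 51%, 75% at ρ = 0.5 and 21%, 41%, 64% at ρ = 0.8. Interaction power is 84-93% at ρ = 0.5 and above 99% at ρ = 0.8. At ρ = 0.3 the ranges are 32-84% for the group effect and 69-82% for the interaction.

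**The case against.** The strongest reply is that the plan does not rest on the group main effect. In a design with a baseline visit, the time-by-group term carries the treatment effect. Section 2.9 plans that term in the same sentence, and baseline does not dilute it. A reader might infer that the planned analysis as a whole loses most of its power. The documents do not support that: no section makes the group effect the deciding test, and the interaction has 84-93% power under the assumptions used here.

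Nor can it be said without conditions that the group effect itself loses most of the power. Neither the SD nor the correlation is stated. At ρ = 0.5 power still reaches 75%, and at ρ = 0.3 with an early effect it is 94%. The lowest figures need no effect at all at month 6. The Intervention section gives clinic sessions twice weekly in the first half-year and once weekly in the second, about two thirds of them by month 6, so a purely late effect is not favoured. If the month-6 effect exceeded the month-12 effect, the group effect could be more than two thirds of the month-12 difference.

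A reader might also infer an inflated false-positive rate. Under 1:1 randomization there is none overall, because chance imbalance is part of the error the test allows for. What remains is the conditional shift in the estimate shown in step 6.

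All of this stands, and it limits the point without removing it. The group effect is still listed on equal footing, with nothing to tell a reader that it does not measure the defined outcomes.

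**Conclusion.** The point holds as a matter of what the term estimates. The dilution follows from the visit schedule alone, and its size (0.15 to 0.31 of 0.46 points) requires only that the month-6 effect lie between nil and the month-12 effect. The loss of power is conditional. It arises only if the group effect is taken as a treatment test, and the 11-75% range depends on an SD of change of 0.50 inferred from the sample size and on an assumed correlation of 0.5-0.8. It is a worthwhile correction to section 2.9. It does not show that the trial is underpowered or that its error rate is inflated.

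**What to change.** In section 2.9:

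- State that the group and time main effects of the three-visit ANOVA are not efficacy tests.
- Model the month-6 and month-12 scores as outcomes, with the baseline score as covariate.
- Report the month-12 between-group contrast as the main treatment estimate for each scale. For MMSE this is the contrast that matches the primary outcome in section 2.5.3.
- Report the month-6 contrast and any pooled effect as supportive. The pooled effect should not lead, because it is itself halved (0.23 of 0.46) if the benefit appears only at month 12.

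The cost is a few sentences. The baseline scores are already collected, and no new data or patients are needed.
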